6.3.4.1 Evaluation of Target Lesions

Complete Response (CR): Disappearance of all target lesions. Any pathological lymph nodes (whether target or non-target) must have reduction in short axis to <10 mm.

Partial Response (PR): At least a 30% decrease in the sum of the diameters of target lesions, taking as reference the baseline sum of diameters.

Progressive Disease (PD): At least a 20% increase in the sum of the diameters of target lesions, taking as reference the smallest sum on study (this includes the baseline sum if that is the smallest on study). In addition to the relative increase of 20%, the sum must also demonstrate an absolute increase of at least 5 mm. (Note: the appearance of one or more new lesions is also considered progressions).

Stable Disease (SD): Neither sufficient shrinkage to qualify for PR nor sufficient increase to qualify for PD, taking as reference the smallest sum of diameters while on study.

6.3.4.2 Evaluation of Non-Target Lesions

Complete Response (CR): Disappearance of all non-target lesions and normalization of tumor marker level. All lymph nodes must be non-pathological in size (<10 mm short axis).

Note: If tumor markers are initially above the upper normal limit, they must normalize for a patient to be considered in complete clinical response.

Non-CR/Non-PD: Persistence of one or more non-target lesion(s) and/or maintenance of tumor marker level above the normal limits.

Progressive Disease (PD): Appearance of one or more new lesions and/or *unequivocal* progression of existing non-target lesions. *Unequivocal progression* should not normally trump target lesion status. It must be representative of overall disease status change, not a single lesion increase.

Although a clear progression of "non-target" lesions only is exceptional, the opinion of the treating physician should prevail in such circumstances, and the progression status should be confirmed at a later time by the review panel (or Principal Investigator).

6.3.4.3 Evaluation of Best Overall Response

The best overall response is the best response recorded from the start of the treatment until disease progression/recurrence (taking as reference for progressive disease the smallest measurements recorded since the treatment started). The patient's best response assignment will depend on the achievement of both measurement and confirmation criteria.

For Patients with Measurable Disease (i.e., Target Disease)

Target Lesions	Non-Target Lesions	New Lesions	Overall Response	Best Overall Response when Confirmation is Required*
CR	CR	No	CR	≥4 wks. Confirmation**
CR	Non-CR/Non- PD	No	PR	≥4 wks. Confirmation**

Version Date: 09/24/2021

Target Lesions	Non-Target Lesions	New Lesions	Overall Response	Best Overall Response when Confirmation is Required*
CR	Not evaluated	No	PR	
PR	Non-CR/Non-PD/not evaluated	No	PR	
SD	Non-CR/Non-PD/not evaluated	No	SD	Documented at least once ≥4 wks. from baseline**
PD	Any	Yes or No	PD	
Any	PD***	Yes or No	PD	no prior SD, PR or CR
Any	Any	Yes	PD	

^{*} See RECIST 1.1 manuscript for further details on what is evidence of a new lesion.

Note: Patients with a global deterioration of health status requiring discontinuation of treatment without objective evidence of disease progression at that time should be reported as "*symptomatic deterioration*." Every effort should be made to document the objective progression even after discontinuation of treatment.

For Patients with Non-Measurable Disease (i.e., Non-Target Disease)

Non-Target Lesions	New Lesions	Overall Response
CR	No	CR
Non-CR/non-PD	No	Non-CR/non-PD*
Not all evaluated	No	not evaluated
Unequivocal PD	Yes or No	PD
Any	Yes	PD

^{* &#}x27;Non-CR/non-PD' is preferred over 'stable disease' for non-target disease since SD is increasingly used as an endpoint for assessment of efficacy in some trials so to assign this category when no lesions can be measured is not advised

6.3.5 Duration of Response

Duration of overall response: The duration of overall response is measured from the time measurement criteria are met for CR or PR (whichever is first recorded) until the first date that recurrent or progressive disease is objectively documented (taking as reference for progressive disease the smallest measurements recorded since the treatment started).

The duration of overall CR is measured from the time measurement criteria are first met for CR

^{**} Only for non-randomized trials with response as primary endpoint.

^{***} In exceptional circumstances, unequivocal progression in non-target lesions may be accepted as disease progression.

Version Date: 09/24/2021

until the first date that progressive disease is objectively documented.

Duration of stable disease: Stable disease is measured from the start of the treatment until the criteria for progression are met, taking as reference the smallest measurements recorded since the treatment started, including the baseline measurements.

6.3.6 Progression Free Survival

Progression Free Survival will be measured from the date of protocol consent until death or progressive disease occurs.

6.4 TOXICITY CRITERIA

The following adverse event management guidelines are intended to ensure the safety of each patient while on the study. The descriptions and grading scales found in the revised NCI Common Terminology Criteria for Adverse Events (CTCAE) version 5.0 will be utilized for AE reporting. All appropriate treatment areas should have access to a copy of the CTCAE version 5.0. A copy of the CTCAE version 5.0 can be downloaded from the CTEP web site (http://ctep.cancer.gov/protocolDevelopment/electronic_applications/ctc.htm).

7 NIH REPORTING REQUIREMENTS/DATA AND SAFETY MONITORING PLAN

7.1 **DEFINITIONS**

Please refer to definitions provided in Policy 801: Reporting Research Events found here.

7.2 OHSRP OFFICE OF COMPLIANCE AND TRAINING/ IRB REPORTING

7.2.1 Expedited Reporting

Please refer to the reporting requirements in Policy 801: Reporting Research Events and Policy 802 Non-Compliance Human Subjects Research found here. Note: Only IND Safety Reports that meet the definition of an unanticipated problem will need to be reported per these policies.

7.2.2 IRB Requirements for PI Reporting at Continuing Review

Please refer to definitions provided in Policy 801: Reporting Research Events found here.

7.3 NCI CLINICAL DIRECTOR REPORTING

Problems expeditiously reported to the OHSRP in iRIS will also be reported to the NCI Clinical Director. A separate submission is not necessary as reports in iRIS will be available to the Clinical Director.

In addition to those reports, all deaths that occur within 30 days after receiving a research intervention should be reported via email to the Clinical Director unless they are due to progressive disease.

To report these deaths, please send an email describing the circumstances of the death to [name] at [contact] within one business day of learning of the death.

7.4 NIH REQUIRED DATA AND SAFETY MONITORING PLAN

7.4.1 Principal Investigator/Research Team

The clinical research team will meet on a weekly basis when patients are being actively treated on the trial to discuss each patient. Decisions about dose level enrollment and dose escalation if applicable will be made based on the toxicity data from prior patients.

Version Date: 09/24/2021

All data will be collected in a timely manner and reviewed by the principal investigator or a lead associate investigator. Events meeting requirements for expedited reporting as described in section 7.2.1 will be submitted within the appropriate timelines.

The principal investigator will review adverse event and response data on each patient to ensure safety and data accuracy. The principal investigator will personally conduct or supervise the investigation and provide appropriate delegation of responsibilities to other members of the research staff.

8 SPONSOR SAFETY REPORTING

8.1.1 Adverse Event

Any untoward medical occurrence in a patient or clinical investigation subject administered a pharmaceutical product and which does not necessarily have a causal relationship with this treatment. An adverse event (AE) can therefore be any unfavorable and unintended sign (including an abnormal laboratory finding), symptom, or disease temporally associated with the use of a medicinal (investigational) product, whether or not related to the medicinal (investigational) product (ICH E6 (R2).

8.1.2 Serious Adverse Event (SAE)

An adverse event or suspected adverse reaction is considered serious if in the view of the investigator or the sponsor, it results in any of the following:

- Death
- A life-threatening adverse event (see **8.1.3**)
- Inpatient hospitalization or prolongation of existing hospitalization
 - A hospitalization/admission that is pre-planned (i.e., elective or scheduled surgery arranged prior to the start of the study), a planned hospitalization for preexisting condition, or a procedure required by the protocol, without a serious deterioration in health, is not considered a serious adverse event.
 - o A hospitalization/admission that is solely driven by non-medical reasons (e.g., hospitalization for patient convenience) is not considered a serious adverse event.
 - Emergency room visits or stays in observation units that do not result in admission to the hospital would not be considered a serious adverse event. The reason for seeking medical care should be evaluated for meeting one of the other serious criteria.
- Persistent or significant incapacity or substantial disruption of the ability to conduct normal life functions
- A congenital anomaly/birth defect.
- Important medical events that may not result in death, be life-threatening, or require hospitalization may be considered a serious adverse drug experience when, based upon appropriate medical judgment, they may jeopardize the patient or subject and may require medical or surgical intervention to prevent one of the outcomes listed in this definition.

Version Date: 09/24/2021

8.1.3 Life-threatening

An adverse event or suspected adverse reaction is considered "life-threatening" if, in the view of either the investigator or sponsor, its occurrence places the patient or subject at immediate risk of death. It does not include an adverse event or suspected adverse reaction that, had it occurred in a more severe form, might have caused death. (21CFR312.32)

8.1.4 Severity

The severity of each Adverse Event will be assessed utilizing the CTCAE version 5.

8.1.5 Relationship to Study Product

All AEs will have their relationship to study product assessed using the terms: related or not related.

- Related There is a reasonable possibility that the study product caused the adverse event. Reasonable possibility means that there is evidence to suggest a causal relationship between the study product and the adverse event.
- Not Related There is not a reasonable possibility that the administration of the study product caused the event.

8.2 ASSESSMENT OF SAFETY EVENTS

AE information collected will include event description, date of onset, assessment of severity and relationship to study product and alternate etiology (if not related to study product), date of resolution of the event, seriousness and outcome. The assessment of severity and relationship to the study product will be done only by those with the training and authority to make a diagnosis and listed on the Form FDA 1572 as the site principal investigator or sub-investigator. AEs occurring during the collection and reporting period will be documented appropriately regardless of relationship. AEs will be followed through resolution.

SAEs will be:

- Assessed for severity and relationship to study product and alternate etiology (if not related to study product) by a licensed study physician listed on the Form FDA 1572 as the site principal investigator or sub-investigator.
- Recorded on the appropriate SAE report form, the medical record and captured in the clinical database.
- Followed through resolution by a licensed study physician listed on the Form FDA 1572 as the site principal investigator or sub-investigator.

For timeframe of recording adverse events, please refer to section **6.1.1**.

8.3 REPORTING OF SERIOUS ADVERSE EVENTS

Any AE that meets protocol-defined serious criteria or meets the definition of Adverse Event of Special Interest that require expedited reporting must be submitted immediately (within 24 hours of awareness) to OSRO Safety using the CCR SAE report form.

All SAE reporting must include the elements described in 8.2.

SAE reports will be submitted to the Center for Cancer Research (CCR) at: [contact] and to the CCR PI and study coordinator. CCR SAE report form and instructions can be found at:

Version Date: 09/24/2021

https://ccrod.cancer.gov/confluence/display/CCRCRO/Forms+and+Instructions

Following the assessment of the SAE by OSRO, other supporting documentation of the event may be requested by the OSRO Safety and should be provided as soon as possible.8.3.

8.4 SAFETY/OTHER REPORTING CRITERIA TO THE PHARMACEUTICAL MANUFACTURER (CTEP)

The NCI Cancer Therapy Evaluation Program (CTEP) is providing clinical grade recombinant human IL-15 for this study. Because the CTEP is responsible for the Clinical Material and Confidential Information which it develops, CTEP must ensure that the Clinical Material and Confidential Information are used, communicated and reproduced appropriately and completely. The PI agrees to use the Clinical Material in accordance with all Federal laws and regulations that govern the use of investigational agents in clinical trials.

The following will be provided to CTEP during the course of the clinical study:

- 1. Initial FDA submission/approval, including: FDA-submitted protocol document; any FDA comments regarding the protocol and IND submission, including correspondence regarding the IND submission safe-to-proceed notice; and, a copy of the FDA acknowledgement of the IND submission(s) stating the IND number, sponsor, title and date of submission.
- 2. Documentation of initial IRB approval of the FDA-submitted protocol document and annual continuing IRB review approvals.
- 3. All significant protocol amendments, including changes in study size, eligibility criteria, study design and end points.
- 4. Notification of any changes in protocol status or other significant events related to the Protocol.
- 5. Notification of any changes in IND status.
- 6. Copies of any FDA communications.
- 7. Copies of IND Annual Reports.
- 8. All IND Safety Reports submitted to the FDA per 21 CFR 312.32. Copies of all IND Safety Reports submitted to the FDA should be forwarded electronically to [contact] (please provide protocol number in subject line).
- 9. Any abstracts, manuscripts, and publications.

Additional safety and efficacy data may also be requested by CTEP to facilitate the development of the Clinical Material across CTEP supported trials.

8.5 REPORTING PREGNANCY

All required pregnancy reports/follow-up to OSRO will be submitted to:

[contact] and to the CCR PI and study coordinator. Forms and instructions can be found here:

https://ccrod.cancer.gov/confluence/display/CCRCRO/Forms+and+Instructions

8.5.1 Maternal Exposure

If a patient becomes pregnant during the course of the study, the study treatment should be discontinued immediately, and the pregnancy reported to the Sponsor no later than 24 hours of when the Investigator becomes aware of it. The Investigator should notify the Sponsor no later

Version Date: 09/24/2021

than 24 hours of when the outcome of the Pregnancy become known,

Pregnancy itself is not regarded as an SAE. However, congenital abnormalities or birth defects and spontaneous miscarriages that meet serious criteria (8.1.2) should be reported as SAEs.

The outcome of all pregnancies (spontaneous miscarriage, elective termination, ectopic pregnancy, normal birth, or congenital abnormality) should be followed up and documented.

8.5.2 Paternal Exposure

Male patients should refrain from fathering a child or donating sperm during the study and for four (4) months after the last dose of IL-15 or alemtuzumab.

Pregnancy of the patient's partner is not considered to be an AE. However, the outcome of all pregnancies (spontaneous miscarriage, elective termination, ectopic pregnancy, normal birth, or congenital abnormality) occurring from the date of the first dose until four (4) months after the last dose should, if possible, be followed up and documented.

8.6 REGULATORY REPORTING FOR STUDIES CONDUCTED UNDER CCR SPONSORED IND Following notification from the investigator, CCR, the IND sponsor, will report any suspected adverse reaction that is both serious and unexpected. CCR will report an AE as a suspected adverse reaction only if there is evidence to suggest a causal relationship between the study product and the adverse event. CCR will notify FDA and all participating investigators (i.e., all investigators to whom the sponsor is providing drug under its INDs or under any investigator's IND) in an IND safety report of potential serious risks from clinical trials or any other source, as soon as possible, in accordance to 21 CFR Part 312.32.

All serious events will be reported to the FDA at least annually in a summary format.

9 CLINICAL MONITORING

As a sponsor for clinical trials, FDA regulations require the CCR to maintain a monitoring program. The CCR's program allows for confirmation of: study data, specifically data that could affect the interpretation of primary and secondary study endpoints; adherence to the protocol, regulations, ICH E6 and SOPs; and human subjects' protection. This is done through independent verification of study data with source documentation focusing on:

- Informed consent process
- Eligibility confirmation
- Drug administration and accountability
- Adverse events monitoring
- Response assessment.

The monitoring program also extends to multi-site research when the CCR is the coordinating center.

This trial will be monitored by personnel employed by a CCR contractor. Monitors are qualified by training and experience to monitor the progress of clinical trials. Personnel monitoring this study will not be affiliated in any way with the trial conduct.

Version Date: 09/24/2021

10 STATISTICAL CONSIDERATIONS

The primary objective of this trial is to determine the safety, toxicity profile, DLT and MTD of rhIL-15 administered at escalating doses s.c. in combination with alemtuzumab. There are three planned dose levels (0.5, 1, and 2 mcg/kg/dose s.c.) and one dosing strategy (weeks 1 and 2 Monday-Friday). In week three all patients will receive alemtuzumab: 3 mg on day 1, 10 mg on day 2, 30 mg on day 3 and 30 mg on Day 5 of the study. The therapy with alemtuzumab will be continued on weeks 4, 5 and 6 on a 3 x weekly schedule at 30 mg for a total of 4 weeks (13 treatments) of alemtuzumab.

The determination of MTD follows the 3+3 design in which 3 to 6 patients will be enrolled in each combination of dose level. In the initial cohort (Cohort 1), at least 3 patients will be enrolled to receive 0.5 mcg/kg/dose of rhIL-15. In Cohort 2, patients will be enrolled to receive 1 mcg/kg/dose of rhIL-15; and in Cohort 3 patients will receive 2 mcg/kg/dose of IL-15.

The MTD will be based on the assessment of DLT during the first 6 weeks of treatment and will be defined as the dose level at which less than one-third of patients (0/3 or 0-1/6 patients) treated at that dose experience a DLT, with the next higher dose level demonstrating a one-third or greater number of patients (≥2/3 or ≥2/6 patients) having DLT. If a patient did not experience DLT and did not finish the 6 weeks of therapy, this patient will not be evaluable for determination of the MTD and will be replaced in the dose level. An additional 3 to 6 patients will be enrolled at the MTD or, if no severe or dose-limiting toxicities are encountered, the maximum administered dose of rhIL-15, so that a total of 9 patients will be treated at this dose to better characterize the clinical activity of rhIL-15 in this patient population. Accordingly, if all dose levels are evaluated (6 patients per dose level with 9 total patients at the MTD or maximum administered dose) a maximum of 21 evaluable patients will be enrolled. Similarly, if all dose levels are evaluated, the minimum number of evaluable patients required will be 15. An additional 9 patients may be enrolled to compensate for inevaluable patients; thus, bringing the maximum accrual ceiling to 30.

It is expected that accrual can be completed in 60 months.

Using this dose escalation scheme, the probability of escalating to the next dose level, based on the true rate of DLT at the current dose, is given by the following table (each group will be considered independently of the other):

True toxicity at a given dose	10%	20%	30%	40%	50%	60%
Probability of escalating	.91	.71	.49	.31	.17	.08

The secondary objectives are first to evaluate the potential antitumor activity of the combination of rhIL-15 and alemtuzumab assessing the clinical response rate and time to progression, Another secondary objective is to characterize the biological effects of rhIL-15 administered with alemtuzumab by FACS analysis to define the percentages and absolute numbers of circulating lymphocytes (T and NK cells) and the T-cell subsets naïve, central and effector memory subsets (based on expression of CD52, CD56, CD4, CD8, CD45RO, CD45RA, CD28, CD95, CD194, and CCR7) by flow cytometry. Finally, a secondary objective is to define the effect of the combination on the plasma levels of proinflammatory cytokines using Mesoscale analysis.

Version Date: 09/24/2021

The secondary objectives of the study include characterize the biological effects of rhIL-15 administered with alemtuzumab on the percentages and absolute number of circulating lymphocytes (T and NK cells) and the T-cell subsets naïve, central and effector memory subsets (based on expression of CD52, CD56, CD4, CD8, CD45 RO, CD45RA, CD28, CD95, CCR7, and CD62L) by flow cytometry, and plasma levels of proinflammatory cytokines. Summary statistics will be reported for these measures and considered exploratory.

The accrual ceiling of 24 participants was determined to include the sample size needed for statistical analysis of the safety, toxicity and maximum tolerated dose in this Phase I trial. It provides for 3 inevaluable participants as well as for an expanded cohort of 9 participants at the maximum tolerated dose.

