3.1.2 Dose Escalation

Dose escalation will proceed in cohorts of 3 to 6 patients. Patients will not begin treatment at the next higher dose level until all patients treated at the previous dose level have completed the DLT evaluation window and an assessment of DLT has been completed.

Patients will receive s.c. rhIL-15 for the initial period Monday-Friday week 1 and 2. They will be assigned to a dose level sequentially based on their order of entry into the study. The starting dose will be 0.5 mcg/kg/dose and in the absence of dose-limiting toxicities dose escalation will proceed to evaluate dose levels of 1.0 and 2.0 mcg/kg/dose. This initial part of the treatment will be 14 days in length and will be followed by 4 weeks (13 treatments) of alemtuzumab. Only toxicities occurring in this 6-week period will be considered in determining dose escalation. Dose-limiting toxicities are defined in Section 3.1.1. Dose-escalation rules are indicated in the table in Section 3.1.2. As just noted, the first 6 weeks of rhIL-15 and alemtuzumab treatment will be considered in defining criteria for dose escalation and the maximum tolerated dose (MTD).

Dose escalation will proceed in cohorts of 3–6 patients. The MTD is the dose level at which no more than 1 of up to 6 patients experience DLT during the first 6 weeks of treatment, and the dose below that at which at least 2 (of \leq 6) patients have DLT as a result of the drug. If a patient did not experience DLT and did not finish treatment, he or she will not be evaluable for toxicity and will be replaced in the dose level. An additional 3 patients may be enrolled to compensate for inevaluable patients.

Dose escalation table:

Dose Escalation Schedule				
Dose Level	Dose of IND Agent*			

Version Date: 09/24/2021

Dose Escalation Schedule			
Level 1 0.5 mcg/kg/dose			
Level 2 1 mcg/kg/dose			
Level 3 2 mcg/kg/dose			
* Doses are stated as exact dose in units (e.g., mg/m², mcg/kg, etc.) rather than as a percentage.			

Dose-escalation rules:

Number of Patients with DLT at a Given Dose Level	Escalation Decision Rule			
0 out of 3	Enter up to 3 patients at the next dose level			
≥ 2	Dose escalation will be stopped. This dose level will be declared the maximally administered dose (highest dose administered). Up to three (3) additional patients will be entered at the next lowest dose level if only 3 patients were treated previously at that dose.			

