1 out of 3	 Enter up to 3 more patients at this dose level. If 0 of these 3 patients experience DLT, proceed to the next dose level. If 1 or more of this group suffer DLT, then dose escalation is stopped, and this dose is declared the maximally administered dose. Up to six (6) additional patients will be entered at the next lowest dose level if only 3 patients were treated previously at that dose. 			
≤1 out of 6 at highest dose level below the maximally administered dose	This is the MTD and is generally the recommended phase 2 dose. At least 9 patients will be entered at the recommended phase 2 dose.			

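### The escalation table does not guarantee Section 10's maximum of 21 evaluable patients: two rows give different step-down sizes for the same result, and one reading reaches 24

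*Combined protocol and SAP*

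**What the plan says.** Section 10 describes a design that "follows the 3+3 design in which 3 to 6 patients will be enrolled in each combination of dose level", with three dose levels. It derives the sample size from "6 patients per dose level with 9 total patients at the MTD or maximum administered dose" and concludes that "a maximum of 21 evaluable patients will be enrolled" and that "the minimum number of evaluable patients required will be 15". It then adds replacements ("An additional 9 patients may be enrolled to compensate for inevaluable patients") and arrives at a ceiling of 30. The Précis and the cohort table in Section 2.3.1.1 also give 30.

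The rules table in Section 3.1.2 governs what happens when a level proves too toxic:

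- The row for two or more DLTs, which gives no denominator: "Up to three (3) additional patients will be entered at the next lowest dose level", provided only 3 were treated there.
- The row for one DLT in three, when the next three patients bring at least one more: "Up to six (6) additional patients will be entered at the next lowest dose level if only 3 patients were treated previously".

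The last row of that table accepts a level as the MTD at no more than 1 DLT in 6. Section 10 words the MTD as fewer than one-third with DLT, spelled out as 0/3 or 0-1/6, with at least 2/3 or 2/6 at the level above.

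On replacements the text is not uniform. Section 3.1.2 allows 3 for inevaluable patients, Section 10 allows 9, and the last paragraph of Section 10 gives a ceiling of 24 that covers 3 inevaluable participants.

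**The concern.** The 6+6+9 sum assumes that only the final dose holds more than six patients. The row that adds up to six at a level previously passed with three allows that level to hold nine before it has been accepted or rejected. If it is then rejected, a second level must still be filled to nine, and 21 is no longer an upper bound.

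What is at stake is the replacement margin. Patients who have no DLT and do not finish the six weeks are replaced, and the ceiling of 30 is justified as 21 evaluable plus 9 replacements. Any shortfall would fall on the last cohort filled. On this path that is the declared MTD, the cohort the expansion is meant to describe best.

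**Working it through.** **Inputs.** Three levels, called L1, L2 and L3 (0.5, 1 and 2 mcg/kg/dose); 3 to 6 patients per level in escalation; the final dose filled to 9 in total (Section 10); step-down of up to 3 or up to 6 (Section 3.1.2). The documents give no expected DLT rates, so the rates in step 5 are assumptions.

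**1. Reproduce the plan's figures.**
- Maximum: 6+6+9 = 21. Minimum: 3+3+9 = 15. Ceiling: 21+9 = 30. Section 10, last paragraph: 21+3 = 24. All agree with the text.
- Probability of escalating, (1−p)³ + 3p(1−p)⁵, for p = 0.1 to 0.6: 0.906, 0.709, 0.494, 0.309, 0.172, 0.082. These match the table in Section 10. That table covers upward moves only and says nothing about stepping down.

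**2. The overlap.** One DLT in three plus at least one in the next three is at least 2 in 6. This meets both the two-or-more row (lower level goes from 3 to 6) and the one-in-three row (lower level goes from 3 to 9).

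**3. A literal path using the larger number.**

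| Step | L1 | L2 | L3 | Total |
|---|---|---|---|---|
| L1 0/3, L2 0/3 | 3 | 3 | 0 | 6 |
| L3 1/3, then 2/6: stop | 3 | 3 | 6 | 12 |
| Six more at L2, 3/9: rejected | 3 | 9 | 6 | 18 |
| Three more at L1, at most 1/6: MTD | 6 | 9 | 6 | 21 |
| L1 filled to 9 | 9 | 9 | 6 | 24 |

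The 3/9 is exactly one-third, so it is not below one-third, and it also meets the two-or-more row. A result of 2/9 (22%) would fail only on the two-or-more row.

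**4. Other readings.** Enumerating every path through the rules:
- Up to six, unstaged, with rejection possible on nine: maximum 24, always split 9, 9, 6.
- Step-down of three on every row, or six staged as 3+3 with the 1-in-6 test between: maximum 9+6+6 = 21.
- Six taken as the expansion of an MTD already declared at L2: at most 6+9+6 = 21.

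**5. How often more than 21 would be needed.** With DLT rates p1, p2, p3, the probability is A × B × C × D:
- A = (1−p1)³[(1−p1)³ + 3p1(1−p1)²] + 3p1(1−p1)⁵ (L1 passed on the way up and accepted at the end)
- B = (1−p2)³ (L2 first passed at 0/3)
- C = 3p3(1−p3)²[1−(1−p3)³] (L3 one in three, then at least one more)
- D = P(Bin(6, p2) ≥ k), with k = 3 if L2 is rejected at one-third or more of 9, and k = 2 if at two or more

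For 10/20/30%: A = 0.8857, B = 0.512, C = 0.2897. D is 0.0989 (k = 3) or 0.3446 (k = 2). The products are 0.0130 and 0.0453.

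| Assumed rates L1/L2/L3 | Rejected at one-third or more | Rejected at 2 or more |
|---|---|---|
| 10/10/30% | 0.30% | 2.14% |
| 10/20/30% | 1.30% | 4.53% |
| 20/30/40% | 1.95% | 4.41% |
| 20/35/50% | 2.08% | 4.02% |
| 10/30/50% | 2.55% | 5.78% |
| 10/40/40% | 2.95% | 4.97% |

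A separate simulation (30,000 runs for each of seven assumed sets, such as 5/15/35% and 10/25/40%) gave 1.0-2.9% and 4.2-6.6%. Taken together: about 0.3-3% under the first rejection rule and 2-7% under the second.

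**6. Against the ceilings.** 30−24 = 6 replacements (20% of 30, against 9 or 30% as planned). 24+9 = 33, above 30. With the 3 replacements of Section 3.1.2, 24+3 = 27, under 30 but over the ceiling of 24 in Section 10's last paragraph.

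**The case against.** The strongest reply is that Section 10 already makes L2 the MTD on this path before any of the six patients enter: it stands at 0/3 with at least 2/6 above it. The six are then the expansion that Section 10 describes, since 3+6 = 9, and the total cannot pass 21. Every MTD criterion in the plan is written for six patients or fewer, and nothing says that DLTs in patients 7 to 9 reverse a declared MTD. The six are also a cap. Entering three, applying the 1-in-6 test and continuing only if it passes complies with the table, and a failing L2 then stops at six.

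This stands as a coherent reading, and 21 holds under it. It does not close the point, because the plan does not commit to it. The table's own MTD row asks for no more than 1 in 6, which 0/3 does not yet show. The two-or-more row carries no denominator. No staging of the six is written down. The consequence of DLTs among them is also left unsaid.

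A reader might infer that the true maximum is 24, that 21 is an arithmetic error, and that 24+9 = 33 breaks the ceiling. The documents do not support that. The 21 follows exactly from its stated premise. The 24 needs two step-downs, all six patients entered unstaged, and rejection on nine. The 9 replacements are permitted, not required, so 24 evaluable patients still fit under 30.

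**Conclusion.** The point holds as an inconsistency in the rules, not as a miscalculation. One result triggers two rows with different step-down sizes; a step-down of three guarantees 21, and a step-down of six does so only if staging or prior declaration of the MTD is assumed. On the literal unstaged reading the bound is 24 evaluable patients, three more than stated, and the replacement margin under 30 falls from 9 to 6.

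The path is uncommon: roughly 0.3% to 7% of trials, depending on the rejection rule and on DLT rates that are assumed here. A shortage under the ceiling of 30 would also need at least seven inevaluable patients. The priority is therefore minor. The conflict between 9 replacements with a ceiling of 30 and 3 replacements with a ceiling of 24 depends on no path or assumed rate, and belongs in the same correction.

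**What to change.** The sponsor should decide which step-down rule is meant and make Section 3.1.2 and Section 10 agree. Either route works:

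- **Keep 21.** Reconcile the two step-down entries so that one result leads to one number. State whether any six patients are entered in stages or are the expansion of an MTD already declared. State what, if anything, DLTs beyond the sixth patient at a level change. Align the MTD wording in the table with that in Section 10.
- **Keep the six unstaged, with rejection possible on nine.** Add the decision rule for nine patients and restate the maximum in Section 10 as 24 evaluable, with 6 replacements within 30.

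In the same edit, give one replacement number and one accrual ceiling throughout: Section 3.1.2 (3 replacements), the main text of Section 10 (9 and 30) and its last paragraph (3 inevaluable and a ceiling of 24).

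The cost is a few sentences and one or two table entries. No extra patients are needed; on the second route the stated replacement margin becomes smaller.
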